7.6. Exploratory Efficacy Endpoints

[figure not shown]

[figure not shown]

[figure not shown]

8. PHARMACOKINETIC ANALYSIS

8.1. Plasma Concentrations

Plasma concentrations of NBI-827104 will be summarized per nominal timepoint overall and by body weight group using the PK analysis set. The number and percentage of subjects with data and the number and percentage of subjects with values below the lower limit of quantification (BLQ) and quantifiable results will be given.

[REDACTED]

All BLQ values will be set equal to zero in the plasma concentration summaries.

8.2. [REDACTED]

[REDACTED]

Table 5: [REDACTED]

9. SAFETY

The safety objective of the study is to characterize the safety profile of NBI-827104 as measured by TEAEs and SAEs, clinical laboratory tests, vital signs, ECG, and the C-SSRS. All outputs for safety endpoints will be based on the safety analysis set. The analysis of the safety data will be based on descriptive statistics and presented by treatment group according to the study visit unless otherwise noted. Data from the neurological and ophthalmic examinations will not be summarized because any abnormal results were assessed for AE reporting by the investigator and will be captured in the AE summaries. Safety data will not be subject to any imputation and will be summarized on an observed case basis. No formal hypothesis-testing analysis of safety data will be performed.

9.1. Study Drug Dosing and Compliance

The duration of exposure to study drug will be calculated as: last dose date – first dose date +1. Duration of exposure will be summarized with descriptive statistics by treatment group.

Dose adjustments will be summarized for each postbaseline visit. The number and percentage of subjects whose dose is escalated, maintained, or reduced will be presented by treatment group. Dose reductions at unscheduled visits will be included in the summary for the next scheduled visit. Subjects who prematurely discontinue study at a visit will not be included in the visit summary unless they had a dose reduction at an unscheduled visit after the previous scheduled visit. The table will include the total number and percentage of subjects with a dose reduction at any time during the treatment period through the end of maintenance. Note that changes in dosage will be presented for the control group, even though no actual changes in study drug are occurring.

A summary of dose levels in subjects in the NBI-827104 treatment group will be presented for each postbaseline visit. Descriptive statistics of the last dose assigned prior to the visit (including at unscheduled visits) will be presented. The number and percentage of subjects receiving each dose will also be presented for each postbaseline visit.

The site will enter into the eCRF whether the subject's dosing compliance since the previous visit was within 80% and 120% inclusive. The number and percentage of subjects in each treatment group who are dosing compliant, <80%, and >120% will be presented for each postbaseline visit.

9.2. Adverse Events

A treatment-emergent adverse event (TEAE) is an AE not present prior to the initiation of study drug dosing, or is an already present event that worsens either in intensity or frequency following the initiation of study drug dosing. Investigators will be asked to respond "Yes" or "No" on the eCRF as to whether the AE started after the subject took the first dose of study drug. An AE with a response of "Yes" will be classified as a TEAE. If the investigator's response is missing, then the treatment emergent status will be derived based on the AE onset date and time relative to the date and time of the subject's first dose of study drug. If the AE onset date and time are unknown, it will be assumed that the AE is a TEAE. If the AE onset time is unknown but the AE onset date is the same date as the first dose of study drug, it will be assumed that the AE is a TEAE. Adverse events with an onset date after the last dose date and on or before the last dose

date plus 14 days will be considered post-treatment emergent and will be tabulated by treatment groups. See details for imputing missing/partial start dates (Section 4.3.5.1). There will be no imputation for AE stop dates.

TEAEs, categorized by MedDRA system organ class (SOC) and/or PT, will be summarized in frequency tables. The frequency tables will include the number and percentage of unique subjects experiencing each event one or more times by treatment group.

An overall summary table will be provided which summarizes the number and percentage of unique subjects with any TEAE, treatment-emergent SAE, TEAE leading to study drug dose reduction, TEAE leading to study drug discontinuation, TEAE leading to study discontinuation, and TEAE resulting in death. The summary table will also include the frequency distribution of the maximum TEAE intensity (mild, moderate, severe) reported for each subject.

The following summary tabulations will also be presented by treatment group. Unless otherwise noted, the tables will be sorted in alphabetical order. The first line of the table will display the number and percentage of subjects with at least one of the following adverse event categories:

- TEAEs, classified by SOC and PT
- Any TEAEs, classified by PT, displayed in a descending order by frequency in the NBI-827104 treatment group
- Treatment-emergent SAEs by SOC and PT
- TEAEs leading to study drug dose reduction by SOC and PT
- TEAEs leading to study drug discontinuation by SOC and PT
- TEAEs leading to study discontinuation by SOC and PT
- TEAEs leading to death by SOC and PT
- Post-treatment emergent AEs by SOC and PT

A listing of TEAEs resulting in study drug discontinuation will be provided which includes subject ID, treatment group, last treatment received prior to the onset time of the TEAEs leading to study drug discontinuation, study day of the discontinuation, and other relevant information from the AE eCRF. Note that “last treatment received prior to the onset time of the TEAEs leading to study drug discontinuation” reflects the actual dose received prior to the AE.

Separate listings of TEAEs resulting in study drug dose reductions, SAEs, and fatal AEs will also be provided. In the event that no subjects experience study drug dose reductions, SAEs, or fatal AEs, the blank listing shell will be presented with text printed in the center of the listing such as “No serious adverse events occurred during this study.”

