#### 11. ADVERSE EVENTS

All AEs, whether observed by the investigator, reported by the subject, noted from laboratory findings, or identified by other means, will be recorded from the time the ICF has been signed until the subject's final study visit (or upon early termination).

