4.3.5. Handling of Missing Data

4.3.5.1. Start Dates for Adverse Events

Missing and incomplete dates for AEs will be imputed for the purpose of estimating the time of the event in relationship to study treatment.

The imputation rules for AE start dates are as follows:

- If the date is completely missing, the date will be imputed as the date of the first dose of study drug;
- If only the day is missing, the date will be imputed as the date of the first dose of study drug if the month and year of the AE start date match the month and year of the first dose of study drug; otherwise, the missing day will be imputed as the first day of the month;
- If both the day and month are missing, the date will be imputed as the date of the first dose of study drug if the AE start date is in the same year as the first dose of study drug; otherwise, the missing day and month will be imputed as 01 January;
- If any of the above imputations result in a start date that is later than an existing (not imputed) end date for the event, the start date will be imputed as the end date.

There will be no imputation for AE stop dates.

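### SAP 9.2 defines a TEAE to include worsening of an event already present, but the rule that sets the flag tests only onset and does not say how a No answer is handled

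*SAP*

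**What the plan says.** SAP 9.2 opens with a definition in two limbs. A TEAE is an AE that was absent before dosing, or one that "is an already present event that worsens either in intensity or frequency following the initiation of study drug dosing".

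The same paragraph then says how the flag is set:

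- The eCRF asks the investigator for a Yes or No "as to whether the AE started after the subject took the first dose of study drug". An AE answered Yes "will be classified as a TEAE".
- If the answer is missing, the "treatment emergent status will be derived based on the AE onset date and time relative to the date and time" of first dose.
- "If the AE onset date and time are unknown, it will be assumed that the AE is a TEAE". An onset on the first-dose date with no time recorded is treated the same way.

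The section also refers to the date imputation in SAP 4.3.5.1. A completely missing start date becomes the date of first dose. If that falls after a recorded end date, "the start date will be imputed as the end date".

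In Protocol 11, all AEs "will be recorded from the time the ICF has been signed", and screening runs from Day -28 to Day -1. Protocol 11.1 counts worsening of a condition present at study start as an AE. Protocol 11.2 gives each AE its own eCRF entry.

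**The concern.** The definition and the rule that implements it are a few lines apart and do not match. Worsening is in the definition, but no step of the rule looks for it. A child whose mild AE began in screening and became severe on treatment meets the definition, yet the truthful answer to the eCRF question is No. The date fallback would give the same result.

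The flag decides which events enter most of the AE tables, and safety and tolerability are the trial's secondary objective. SAP 9 adds weight: neurological and ophthalmic examination data will not be summarised separately, on the ground that the AE summaries will capture abnormal results.

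A smaller mismatch runs in the opposite direction. An AE of unknown onset is assumed to be treatment-emergent, even where a recorded end date shows that it was over before dosing began.

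**Working it through.** The documents give no figure to reproduce. The check traces each type of event through the definition and then through the flag rule in SAP 9.2.

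| Case | By the definition | By the flag rule | Agree? |
|---|---|---|---|
| (a) Onset after first dose | TEAE | Answer Yes: TEAE | Yes |
| (b) Onset in screening, unchanged on treatment | Not a TEAE | Answer No: no route to TEAE. Answer missing: onset precedes dosing, not a TEAE | Yes |
| (c) Onset in screening, worse after first dose, kept on its original entry | TEAE (second limb) | Answer No: no route to TEAE. Answer missing: onset precedes dosing, not a TEAE | **No** |
| (d) As (c), but the worsening entered as a new AE with its own later onset | TEAE | Answer Yes: TEAE | Yes |
| (e) Answer missing, onset unknown, recorded end date before first dose | Not a TEAE | Unknown-onset default: TEAE | **No** |

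Case (c) is the main gap. It depends on whether sites work as in (c) or as in (d). Protocol 11.2 does not settle this: it asks for one entry per AE and does not say to open a new one when an AE already recorded gets worse.

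Case (e) also sets SAP 9.2 against SAP 4.3.5.1. Under 4.3.5.1 the start is first imputed as the date of first dose. That is later than the recorded end date, so the start is reset to the end date. The end date precedes dosing, so the imputed onset implies that the event is not a TEAE, whereas the default in 9.2 says that it is.

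**Which outputs are affected in case (c).** From SAP 9.2:

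- Dependent on the flag: any TEAE, the tables by system organ class and preferred term, maximum intensity, treatment-emergent SAEs, and TEAEs leading to dose reduction, to discontinuation of drug or study, or to death.
- Not dependent on it: the post-treatment emergent table, which is set by onset after the last dose. The SAE and fatal-AE listings may also still show the event.

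**Scale of one missed child.** The inputs are the planned allocations in SAP 3.1:

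- Active arm: 4 (sentinel) + 18 × 2/3 (main) = 4 + 12 = 16, so one child is 1/16 = 6.25 percentage points.
- Placebo arm: 2 (sentinel) + 18 × 1/3 (main) = 2 + 6 = 8, so one child is 1/8 = 12.5 percentage points.

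The tables count unique subjects. A row therefore moves by this amount only if the missed event was that child's only event in the row. The documents give no rate of screening-onset AEs that later worsen, so the number of children affected cannot be calculated.

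**The case against.** **No is not defined.** The SAP makes Yes sufficient for a TEAE and never says that No excludes an event. The two-limb definition could be read as still governing. A reader might infer a written rule that excludes worsened events, and there is none. The exclusion is implied, because only Yes, a missing answer or an unknown onset leads to TEAE status. That stands as a limit on the wording, but a programmer still has to fill the gap, and every step provided points to onset.

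**Worsening is already an AE under the protocol.** Protocol 11.1 treats worsening of a condition present at study start as an AE, and treats a persistent pre-dose symptom as an AE only if it progresses after dosing. For such conditions the AE naturally starts at the worsening and the answer is Yes. So a reader should not infer that every pre-existing condition that worsens is lost. The gap is mainly AEs already recorded as AEs between consent and first dose.

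**Data checks exist.** Protocol 12.2 provides automated date-consistency checks, manual review and queries. It would be wrong to infer that a No is never compared with a recorded onset date. The documents do not describe that particular check, but individual edit checks need not appear in a protocol or SAP.

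**The loss is partial.** A reader might infer that every AE output depends on the flag. The post-treatment emergent table does not, and the SAE and fatal-AE listings may still show the event. Reasons for stopping study drug (SAP 5.1) and dose adjustments (SAP 9.1) are also tabulated without it. Safety is descriptive, with no hypothesis tests.

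**Unknown onset is a rare case.** Read in sequence, it needs a missing answer, an unknown onset and a known pre-dose end date together, and the default is conservative. That is fair, but the two sections still give different answers.

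**Conclusion.** The point holds in a bounded form. The flag rule in SAP 9.2 omits one of the two limbs of the definition and leaves No unspecified. An AE recorded in screening that worsens on treatment would be left out of the TEAE tables if it stays on its original entry. Neither document tells sites to re-enter or flag it.

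This rests on two assumptions: that No is programmed as not treatment-emergent, and that sites do not open a new record at worsening. The eCRF completion instructions are not among the documents, so the second cannot be confirmed.

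The number affected is unknown and limited to AEs starting between consent and first dose. At the planned arm sizes, a missed child shifts a row by 6.25 points (active) or 12.5 points (placebo), subject to the unique-subject condition above. The change should be made because it decides which events are counted for the secondary objective, and it costs little.

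**What to change.** 1. Add to SAP 9.2 that an AE answered No is still a TEAE if its intensity or frequency increases after first dose, and apply the same test when the answer is missing. Keep to intensity and frequency, the two criteria in the SAP's own definition.
2. Instruct sites to enter such worsening as a new AE record dated at the worsening. This gives the SAP rule data to work on, since neither document describes recording a change in intensity or frequency within one entry.
3. Query any No that carries a recorded onset after first dose. The investigator should resolve the query; the onset date should not override the answer automatically.
4. State that an AE of unknown onset with a known end date before first dose is not a TEAE, so that SAP 9.2 agrees with 4.3.5.1.

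The cost is a few sentences in the SAP, one eCRF instruction and one edit check. The TEAE count may rise slightly. SAP 1 requires analysis decisions to be settled before database lock and unblinding, so the change belongs before then. If sites have already recorded data, AEs with onset before first dose that were still ongoing at first dose can be reviewed blind and queried in the same window.

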#### 2. SYNOPSIS

Title of study: Phase 2 Multicenter, Randomized, Double-Blind, Placebo-Controlled, Parallel-Group Study to Assess the Efficacy, Safety, Tolerability, and Pharmacokinetics of NBI-827104 in Pediatric Subjects with Epileptic Encephalopathy with Continuous Spike-and-Wave During Sleep Protocol number: NBI-827104-CSWS2010 Phase of development: 2 Study center(s): Approximately 24 study centers in regions including, but not limited to, the United States, Europe, and Canada **Primary Objective:** To assess the effect of NBI-827104 on the overnight epileptiform video-electroencephalogram (video-EEG) activity in pediatric subjects with epileptic encephalopathy with continuous spike-and-wave during sleep (EECSWS) **Secondary Objective:** To evaluate the safety and tolerability of multiple doses of NBI-827104 in pediatric subjects with **EECSWS Other Objectives:** Methodology: This is a Phase 2, multicenter, double-blind, placebo-controlled, parallel-group study designed to assess the efficacy, safety, tolerability, and PK of NBI-827104 in pediatric subjects with EECSWS. Approximately 24 male and female subjects, 4 to 12 years of age (inclusive), will be enrolled for study participation. Treatment will be administered for up to including titration and taper periods. After providing parental or legal guardian informed consent with pediatric assent from developmentally capable pediatric subjects, subjects will be screened to determine eligibility (Days -28 to -1) before the start of study treatment dosing on Day 1. Caregiver(s) will be given a seizure diary at screening, Day 1, and and caregiver(s) will return the seizure diary at the next scheduled visit. At least 4 days of baseline seizure diary data should be obtained prior to randomization. On Day 1, eligible subjects who have a diagnosis confirmed by an external Diagnosis Confirmation Panel (DCP) will return to the study center for collection of baseline safety and efficacy assessments. Subjects who are confirmed as eligible will then be randomized to NBI-827104 or placebo. The first 6 subjects (randomized 2:1; ie, 4 subjects randomized to NBI-827104 and 2 subjects randomized to placebo) will be enrolled into a sentinel cohort for the analysis of safety, tolerability, and PK data through the end of followed by the remaining 18 subjects in the main cohort (randomized 2:1 [NBI-827104:placebo]). Study treatment will last for up to If an open-label extension (OLE) study is open for enrollment, eligible subjects may enter the OLE study following the completion of the study visit at the end of the maintenance period. For subjects who enroll directly in the OLE study, the visit will be the final study visit of the current study. For all other subjects, the end of the posttreatment safety period constitutes the end of the study.

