#### 7. STUDY DESIGN

This is a Phase 2, multicenter, double-blind, placebo-controlled, parallel-group study designed to assess the efficacy, safety, tolerability, and PK of NBI-827104 in pediatric subjects with EECSWS. Approximately 24 male and female subjects, aged 4 to 12 years (inclusive), will be enrolled for study participation. Treatment will be administered for up to including titration and taper periods.

After providing parental or legal guardian informed consent with pediatric assent from developmentally capable pediatric subjects, subjects will be screened to determine eligibility (Days -28 to -1) before the start of study treatment dosing on Day 1. Caregiver(s) will be given a seizure diary at the next scheduled visit. At least 4 days of baseline seizure diary data should be obtained prior to randomization. On Day 1, eligible subjects who have a diagnosis confirmed by an external Diagnosis Confirmation Panel (DCP) will return to the study center for collection of baseline safety and efficacy assessments. Subjects who are confirmed as eligible for the study will then be randomized to NBI-827104 or placebo. The first 6 subjects (randomized 2:1; ie, 4 subjects randomized to NBI-827104 and 2 subjects randomized to placebo) will be enrolled into a sentinel cohort for the analysis of safety, tolerability, and PK data through the end of followed by the remaining 18 subjects in the main cohort (randomized 2:1 [NBI-827104:placebo]). Study treatment will last for up to

If an open-label extension (OLE) study is open for enrollment, eligible subjects may enter the OLE study following the completion of the study visit at the end of the maintenance period. For subjects who enroll directly in the OLE study, the visit will be the final study visit of the current study. For all other subjects, the end of the posttreatment safety period constitutes the end of the study.

[figure not shown]
The starting dose of study treatment for the sentinel cohort (dose level 1) will be based on body weight categories (based on subjects' body weight on Day 1), as detailed in Table 1. This study intends to target exposures equivalent to those observed

in adults

[figure not shown]
Based on the exposure

data obtained from the sentinel cohort, the doses may be adjusted if required to achieve the targeted exposure in the main cohort.

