4.2. Analysis Sets

The following analysis sets are defined for this study in [Table 4](#).

Table 4: Analysis Sets

Analysis Sets	Description
Full Analysis Set	The full analysis set includes all randomized subjects who took at least one dose of study treatment and have at least one efficacy video-EEG assessment. Subjects will be analyzed according to their randomized treatment group.
Safety Analysis Set	The safety analysis set includes all subjects who received at least one dose of study treatment. Subjects will be analyzed according to the study treatment they received.
Pharmacokinetic (PK) Analysis Set	The PK analysis set comprises all subjects included in the safety analysis set who had at least one evaluable plasma concentration after initiation of NBI-827104 and did not deviate from the protocol in a way that might affect the evaluation of the PK endpoint.
Per-protocol Analysis Set	This analysis set includes all randomized subjects who completed at least 6 weeks of treatment without protocol deviations that may affect the evaluation of the primary endpoint. Subjects will be analyzed according to their randomized treatment group.

Summaries of subject disposition, analysis set inclusion/exclusion status, and important protocol deviations (IPD) will be based on all randomized subjects. Efficacy summaries and demographics/baseline characteristics are based on the full analysis set. The PK analysis set will be employed in the analysis of the plasma concentrations and PK parameters. All other summaries are based on safety analysis set unless otherwise noted.

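### Post-treatment AE percentages use everyone dosed as the denominator, although children who go straight into the open-label extension have no planned AE collection after their last dose

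*SAP*

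**What the plan says.** **Denominator.** SAP 9 states: "All outputs for safety endpoints will be based on the safety analysis set". SAP 4.2 defines that set: "The safety analysis set includes all subjects who received at least one dose of study treatment". Observation after the last dose is not required.

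**Table.** SAP 9.2 places onset after the last dose, and up to the last-dose "date plus 14 days will be considered post-treatment emergent and will be tabulated by treatment groups". The list of AE tables in that section includes "Post-treatment emergent AEs by SOC and PT". The lead-in to the list fixes the statistic: "The first line of the table will display the number and percentage of subjects with at least one of the following adverse event categories". No separate denominator is given for the post-treatment table.

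**Who is followed.** Protocol 7 says that, if an OLE is open, "eligible subjects may enter the OLE study following the completion of the study visit at the end of the maintenance period". The Synopsis adds (visit label redacted): "For subjects who enroll directly in the OLE study, the visit will be the final study visit of the current study". Protocol 11 says that AEs "will be recorded from the time the ICF has been signed until the subject's final study visit (or upon early termination"). Protocol 9.6 includes a posttreatment safety period in the study duration of children who do not enroll directly in an OLE, and none for those who do.

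**The concern.** A percentage of subjects with an event in a time window is informative only if the children in the denominator were watched during that window. Here a child who moves directly into the OLE is counted in the same way as a child who was followed for 14 days and had no event.

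Safety and tolerability is the secondary objective. Under Protocol 11.1, a significant increase in seizure frequency, a new seizure type or status epilepticus can count as an AE. This table is the one dedicated to such events after dosing stops. If many children roll over, the printed percentages are low partly because few children were observed. If rollover differs by arm, the comparison between arms moves for a reason unrelated to the drug.

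The planned outputs do not let a reader undo this. The disposition summary in SAP 5.1 lists completion and discontinuation categories, but neither OLE entry nor follow-up after the last dose. The number at risk per arm therefore cannot be rebuilt from it.

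**Working it through.** The plan states no post-treatment AE rate and no rollover rate, so there is no figure to reproduce. What can be checked is the arithmetic that the stated denominator implies.

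**Inputs from the documents.** Protocol 8.4 gives a sentinel cohort of 6 (4 NBI-827104, 2 placebo) and a main cohort of 18 randomized 2:1 (12 and 6). Arm sizes are 4 + 12 = 16 and 2 + 6 = 8, total 24, which matches the planned number.

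**Assumptions.** All randomized children are dosed. Every child who does not enter the OLE directly is followed after the last dose. Rollover is varied because it is not stated.

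**Formula.** Let N be the children dosed in an arm, m the number followed after the last dose, x the number with an event, and f = 1 − m/N the rollover fraction. Then

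displayed rate = x/N = (x/m) × (m/N) = rate among those followed × (1 − f).

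**One child with an event, per arm:**

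| Arm | Roll over | Followed | As planned | Among followed | Multiplier 1 − f |
|---|---|---|---|---|---|
| NBI-827104 | 0 | 16 | 1/16 = 6.3% | 1/16 = 6.3% | 1.00 |
| NBI-827104 | 4 | 12 | 6.3% | 1/12 = 8.3% | 0.75 |
| NBI-827104 | 8 | 8 | 6.3% | 1/8 = 12.5% | 0.50 |
| NBI-827104 | 12 | 4 | 6.3% | 1/4 = 25.0% | 0.25 |
| Placebo | 0 | 8 | 1/8 = 12.5% | 1/8 = 12.5% | 1.00 |
| Placebo | 2 | 6 | 12.5% | 1/6 = 16.7% | 0.75 |
| Placebo | 4 | 4 | 12.5% | 1/4 = 25.0% | 0.50 |
| Placebo | 6 | 2 | 12.5% | 1/2 = 50.0% | 0.25 |

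**Between arms.** If the rate among those followed is the same in both arms, the displayed ratio (NBI-827104 over placebo) is (1 − f for NBI-827104)/(1 − f for placebo):

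- 50% rollover in both arms: 0.50/0.50 = 1.0, no distortion.
- 75% on NBI-827104 and 50% on placebo: 0.25/0.50 = 0.50.
- 50% on NBI-827104 and 75% on placebo: 0.50/0.25 = 2.0.

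**Zero events.** The exact one-sided 95% upper bound for 0 of n is 1 − 0.05^(1/n):

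- n = 16: 17.1%.
- n = 8: 31.2%.
- n = 4: 52.7%.

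A printed 0/16 therefore claims more than the data hold if only 8 or 4 children were followed.

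**Practice elsewhere in the SAP.** For the laboratory shift tables, SAP 9.3 leaves out children without baseline or postbaseline values and takes percentages of those included. SAP 9.6 does the same in the C-SSRS shift tables by dropping children with missing scores. The post-treatment AE table has no such rule.

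**The case against.** - **The denominator comes from a general rule.** The sentence defining these AEs says only that they are tabulated, and SAP 9 also says that safety data are summarized on an observed-case basis. This does not remove the point. Observed-case handling rules out imputation but does not define who is at risk for an AE count. SAP 9 covers all safety outputs, and SAP 9.2 makes no exception.
- **The size is unknown.** This stands. The OLE is conditional and open only to eligible children, so dilution may be nil. A reader might infer a large fixed understatement, even tenfold. That would need 90% rollover, or 14.4 of 16 children, and nothing in the documents supports such a rate.
- **Other off-drug follow-up exists.** This stands. A reader might infer that the posttreatment period is the only off-drug observation. Protocol 9.8 and 9.8.1 keep children who stop dosing early in the study, so they too are seen off drug.
- **The table is not a full account of drug withdrawal.** This stands. Taper doses precede the last dose, so taper events fall outside the window. The table covers only the 14 days after the last dose.
- **Events are not hidden.** This largely stands. The TEAE definition in SAP 9.2 has no end date, counts appear beside percentages, and SAEs are listed. Protocol 11.4 also requires notification of related SAEs learned of after a child's final visit. What is lost is the number at risk.
- **Restricting the denominator does not recover a true rate.** This stands. Children who decline, are ineligible for or never reach the OLE are a selected group, and selection may differ by arm.
- **Redaction.** The text of Protocol 9.5.4 and 9.5.5 and of SAP section 11 is not visible, so further handling there cannot be excluded.

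**Conclusion.** The point holds as a denominator problem in one descriptive table. As written, SAP 9 and 9.2 count direct OLE entrants as event-free in a window in which this study plans no AE collection for them. The printed percentage is the rate among children followed times the fraction followed: unchanged with no rollover, and 0.75, 0.50 or 0.25 of that rate at an assumed 25%, 50% or 75%. The between-arm ratio is affected by the denominator only if rollover is unequal.

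These figures rest on 16 and 8 children dosed, on assumed rollover, and on follow-up of every child who does not roll over. A reader might take the rate among those followed as the rate for all treated children. The documents do not support that, because nothing shows that children who roll over would have the same risk. No hypothesis test and no efficacy result depends on this table, but it bears on the secondary objective and is easily put right before database lock.

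**What to change.** In SAP 9.2, state that percentages in the table of post-treatment emergent AEs by SOC and PT are based on safety-set children with any follow-up in this study after their last dose. Include early discontinuers who remain in the study. Print that n for each arm in the column header.

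Add two footnotes:

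- the number of direct OLE entrants in each arm;
- a statement that the followed group is selected, so the rate describes the children followed and not all treated children.

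The cost is one sentence, two footnotes and one denominator flag built from dosing, visit and disposition data, with no new data collection. The downside is a smaller denominator and less precision for this one table.
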